10.2. Schedule of Assessments

10.2.1. Screening Period

The Screening Period begins at the time of consent/assent of the study subject. Subjects whose parents/guardians have provided written informed consent (and assent for subjects ≥ 7 years of age or as permitted by local IRB and state requirements) will be assigned a unique study subject number and the following screening procedures will be conducted:

- Evaluation of study eligibility requirements.
- Urine pregnancy test (females of childbearing potential only).
- Review of medical history and concomitant medications.
- Body temperature (obtained in the site's usual fashion).

Eligible subjects will be enrolled. The study pharmacist will prepare an order for study drug as defined in Section 11.4, which includes the subject's study number.

10.2.2. Treatment Period

Randomization (prior to the approval of amendment 3) and study drug administration should begin as soon as possible following determination that the subject is eligible for enrollment at Screening. Therefore, it is anticipated that the date of Screening/Baseline and Day 1 (date of administration of the first dose of study medication) will be the same day. Day 1 represents the first day of dosing. Subjects will receive IV peramivir in a single dose or oral oseltamivir BID for five days. *Note, following the approval of amendment 3, no additional subjects will be randomized to receive oseltamivir.*

10.2.2.1. Day 1/Baseline/Pre-Dose

The following procedures/evaluations will be performed pre-dose at Baseline on Day 1:

• Body temperature just prior to study drug administration (using the study electronic thermometer via the oral or axillary method).

- Physical examination, including assessment of presence of possible influenza-related complications.
- Vital sign measurements (blood pressure (in children < 2 only if clinically indicated), heart rate, respiration rate).
- Review and recording of concomitant medications.
- Blood specimen collection for clinical chemistry and clinical hematology tests as specified in Sections 11.2.1 and 11.2.2 and a serum sample for future influenza antibody analysis. Subjects whose weight is < 10kg do not require a serum antibody sample.

(Clinical laboratory specimens collected at Screening are for the purpose of establishing a baseline and the results are not required to determine subject eligibility).

- Urine sample collection for routine urinalysis.
- Determination (and recording in the Subject Diary) of the presence and severity of each of the age specific symptoms of influenza (see Section 10.1). Questions asked of subjects age 6 years and older, if possible.
- Determination [with assistance from the subject (if possible)] of the subject's ability to perform usual daily activities.
- Determination [with assistance from the subject (if possible)] of the subject's appetite and eating patterns assessed as either normal or reduced/abnormal.
- Bilateral adequate nasal swab specimen collection for viral subtyping, culture, quantitative PCR assay and susceptibility to neuraminidase inhibitors.
- Administration of the study medication (at Hour 0) and recording of the calendar date and 24-hour clock time for the start and finish of the IV infusion, if applicable. Each subject will receive peramivir, if ≤ 12 then adjusted for body weight, and oseltamivir adjusted for weight in subjects ≤ 12.

10.2.2.2. Day 1/Post-Dose

The following procedures/evaluations will be performed post-dose on Day 1:

- For subjects randomized to peramivir: collection of up to 4 plasma samples, where possible, during the following time periods, beginning from the end of dosing until release from the site. For each plasma sample the calendar date and 24-hour clock time of sample collection will be recorded:
 - 1. One time point immediately following completion of the infusion
 - 2. One time point from 30 minutes to 1 hours post-infusion
 - 3. One time point from 1 hour to 3 hours post-infusion
 - 4. One time point from 3 hours to 6 hours post-infusion

Note: Subjects ≥ 5 kg will have four 1.0 mL blood draws at the above stated sampling times. Subjects ≤ 5 kg will have two 1.0 mL blood samples; one time immediately following completion of the infusion and one time between 1-3 hours post-infusion.

- Training of the parent/ caregiver and the recording of the following in the Subject Diary:
 - Subject's body temperature, obtained at approximately 12-hour intervals each day (and 4 hours from last antipyretic medication administration or immediately prior to administration).
 - Subject's ability to perform usual activities, obtained once daily.
 - Subject's appetite and eating patterns assessed as either normal or reduced/abnormal.
 - The age specific signs and symptoms of influenza (see Section 10.3.2).
- Review and recording concomitant medications.
- Recording of AEs.

10.2.2.3. Day 3

The following procedures/assessments will be performed on Day 3. The Day 3 assessment may be performed in the subject's home by a qualified study nurse, or as a clinic visit.

- Body temperature (using the study electronic thermometer via the oral or axillary method).
- Assessment of presence of possible influenza-related complications.
- Vital sign measurements (blood pressure (in children < 2 only if clinically indicated), heart rate, respiration rate).
- Review of the Subject Diary for completeness and instruction to the parent/caregiver on need to ensure complete recording of required assessments, if needed.
- Determination (and recording in the Subject Diary) of the presence and severity of each of the age specific symptoms of influenza. Questions asked of subjects age 6 years and older, if possible.
- Determination (and recording in the Subject Diary) [with assistance from the subject (if possible)] of the subject's ability to perform usual daily activities.
- Determination (and recording in the Subject Diary) of the subject's appetite and eating patterns assessed as either normal or reduced/abnormal.
- Bilateral adequate nasal swab specimen collection for viral culture and quantitative PCR assay.
- Review and recording of concomitant medications.
- Recording of AEs.

10.2.2.4. Day 7

The following procedures/assessments will be performed on Day 7 (+ 2 days). The Day 7 assessment will be performed as a clinic visit.

- Urine pregnancy test (females of childbearing potential only).
- Body temperature (using the study electronic thermometer via the oral or axillary method).
- Blood specimen collection for clinical chemistry and clinical hematology tests as specified in Sections 11.2.1 and 11.2.2 and a serum sample for future influenza antibody analysis. Subjects whose weight is < 10kg do not require a serum antibody sample.
- Urine collection for urinalysis
- Assessment of presence of possible influenza-related complications.
- Vital sign measurements (blood pressure (in children < 2 only if clinically indicated), heart rate, respiration rate).
- Review of the Subject Diary for completeness and instruction to the parent/caregiver on need to ensure complete recording of required assessments, if needed.
- Determination (and recording in the Subject Diary) of the presence and severity of each of the age appropriate symptoms of influenza. Questions asked of subjects age 6 years and older, if possible.
- Determination (and recording in the Subject Diary) [with assistance from the subject (if possible)] of the subject's ability to perform usual daily activities.
- Determination (and recording in the Subject Diary) of the subject's appetite and eating patterns assessed as either normal or reduced/abnormal
- Bilateral adequate nasal swab specimen collection for viral culture, quantitative PCR assay and susceptibility to neuraminidase inhibitors.
- Review and recording of concomitant medications.
- Recording of any AEs.

10.2.2.5. Day 14

The following procedures/assessments will be performed on Day 14 (+ 3 days). The Day 14 assessments will be performed as a clinic visit, home visit (conducted by a qualified study nurse) or, if either of these options are not possible, by phone call. If conducted by phone, the Day 14 assessments will be limited to interview assessment for the presence of possible influenza-related complications, concomitant medication use and AEs. The subject's parent/ caregiver will be asked to return the completed Subject Diary by mail.

- Body temperature (using the study electronic thermometer via the oral or axillary method).
- Assessment of presence of possible influenza-related complications.

- Vital sign measurements (blood pressure (in children < 2 only if clinically indicated), heart rate, respiration rate).
- Review of the Subject Diary for completeness.
- Determination (and recording in the Subject Diary) of the presence and severity of each of age appropriate symptoms of influenza. Question asked of subjects age 6 years and older, if possible.
- Determination (and recording in the Subject Diary) [with assistance from the subject (if possible)] of the subject's ability to perform usual daily activities.
- Determination (and recording in the Subject Diary) of the subject's appetite and eating patterns assessed as either normal or reduced/abnormal
- Bilateral adequate nasal swab specimen collection for viral culture, quantitative PCR assay and susceptibility to neuraminidase inhibitors.
- Review and recording of concomitant medications.
- Recording of any AEs.
- If previous lab results are abnormal and considered clinically significant by the Investigator or significantly changed from baseline, blood specimen collection for clinical chemistry or clinical hematology tests as specified in Sections 11.2.1 and 11.2.2 may be drawn.
- If previous lab results are abnormal and considered clinically significant by the Investigator or significantly changed from baseline, urine collection for urinalysis may be completed.

10.2.2.6. Early Withdrawal

For subjects who withdraw before the Day 7 assessment, the following procedures/assessments will be performed at an Early Withdrawal visit, where possible. Assessments will be performed as a clinic visit or home visit (conducted by a qualified study nurse). For subjects who withdraw between the Day 7 and day 14 assessments, a phone assessment will be performed, where possible. A phone assessment will be limited to interview assessment for the presence of possible influenza-related complications and AEs. The subject's parent/caregiver will be asked to return the completed Subject Diary by mail.

- Urine pregnancy test (females of childbearing potential only).
- Body temperature (using the study electronic thermometer via the oral or axillary method).
- If previous lab results are abnormal and considered clinically significant by the Investigator or significantly changed from baseline, blood specimen collection for clinical chemistry or clinical hematology tests as specified in Sections 11.2.1 and 11.2.2 may be drawn

- If previous lab results are abnormal and considered clinically significant by the Investigator or significantly changed from baseline, urine collection for urinalysis may be completed
- Assessment of presence of possible influenza-related complications.
- Vital sign measurements (blood pressure (in children < 2 only if clinically indicated), heart rate, respiration rate).
- Review of the Subject Diary for completeness.
- Determination (and recording in the Subject Diary) of the presence and severity of each of the age appropriate symptoms of influenza. Questions asked of subjects age 6 years and older, if possible.
- Determination (and recording in the Subject Diary) [with assistance from the subject (if possible)] of the subject's ability to perform usual daily activities.
- Determination (and recording in the Subject Diary) of the subject's appetite and eating patterns assessed as either normal or reduced/abnormal
- Bilateral adequate nasal swab specimen collection for viral culture, quantitative PCR assay and susceptibility to neuraminidase inhibitors.
- Review and recording of concomitant medications.
- Recording of any AEs.

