7. INVESTIGATIONAL PLAN

7.1. Endpoints

7.1.1. Primary Endpoint

The primary endpoints of this study will be assessment of adverse events, laboratory analyses (clinical chemistry, hematology and urinalysis), vital signs and physical examinations.

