- 16 Any subject with unresolved moderate or severe intensity influenza symptoms or an unresolved AE and/or treatment-emergent laboratory finding that requires further medical management may be evaluated in further follow-up visits, at the Investigator's discretion.
- 17 If previous lab results are abnormal and considered clinically significant by the Investigator or significantly changed from baseline, blood specimen collection for clinical chemistry or clinical hematology tests as specified in Sections 11.2.1 and 11.2.2 may be drawn. If previous urinalysis lab results are abnormal and considered clinically significant by the Investigator or significantly changed from baseline, a urine collection for urinalysis may be completed.

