8.3. Withdrawal Criteria

Participation in the study is strictly voluntary. Parents/guardians have the right to withdraw their children from the study at any time and for any reason. A subject's participation will be terminated:

- At their parent's/guardian's request;
- At the subject's request if ≥ 7 years old and able to give assent; in cases where a subject is < 7 years of age and expresses a wish to stop the study, the parent/caregiver and the Investigator will use their best judgments to determine what is in the best interest for the child in question;
- If, in the Investigator's or Sponsor's opinion, continuation in the study would be detrimental to the subject's well-being;
- If the subject is not able to comply with the study requirements;

- If the Sponsor terminates the study;
- If a regulatory authority requires that all study activities be halted.

In all cases, the reason for withdrawal must be recorded in the subject's medical records (source documents). If the reason for subject withdrawal is not known, the subject must be followed to establish whether the reason was an AE, and if so, this must be reported in accordance with the procedures outlined in Section 11.1.2. Vigorous attempts should be made for follow-up of all subjects who miss a study visit. In general, although study drug may be stopped, subjects will be encouraged to complete the scheduled procedures. The subject will require an Early Withdrawal Visit if withdrawn from the study prior to scheduled study completion. If a subject's participation in this study is terminated, the responsible Investigator at the site will complete a termination form.

To the extent possible, all scheduled end-of-study assessments (including the Early Withdrawal Visit) should be performed on all participating subjects who withdraw from the study before the Day 7 Visit. For subjects who withdraw between Day 7 and Day 14, a telephone assessment should be conducted, where possible.

Subjects withdrawn from the study at any time other than during the screening period will not be replaced.

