11.2.1. Clinical Chemistry Profiles

Clinical chemistry profiles will include a Chemistry 20 panel (includes sodium, potassium, chloride, total CO₂ [bicarbonate], creatinine, glucose, urea nitrogen, albumin, total calcium, total magnesium, phosphorus, alkaline phosphatase, alanine aminotransferase (ALT), aspartate aminotransferase (AST), total bilirubin, direct bilirubin, lactate dehydrogenase (LDH), total protein, total creatine kinase, and uric acid).

Blood samples for clinical chemistry profiles will be collected at Baseline and at the Day 7 follow-up assessment. Clinically significant results should be reported as AEs.

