13.9. Safety Analyses

Adverse Events will be mapped to a Medical Dictionary for Regulatory Activities (MedDRA)-preferred term and system organ classification. The occurrence of treatment-emergent AEs (TEAEs) will be summarized by age group and treatment group using MedDRA-preferred terms, system organ classifications, and severity. All AEs will be listed for individual subjects showing both verbatim and preferred terms. Separate summaries of treatment-emergent SAEs and AEs related to study drug will be generated.

Descriptive summaries of vital signs and clinical laboratory results will be presented by age group, treatment group and study visit. Laboratory abnormalities will be graded according to the DAIDS Table for Grading Adverse Events for Adults and Pediatrics (Publish Date: December 2004 Clarification, 2009, see Appendix 1). The number and percentage of subjects experiencing treatment-emergent graded toxicities will be summarized by age group and treatment group. Laboratory toxicity shifts from baseline to post-baseline assessments will be summarized by age group and treatment group.

Previous and concomitant medications will be mapped to a WHO preferred term and drug classification. The number and percent of subjects taking concomitant medications will be summarized using preferred terms and drug classifications.

The number and percent of subjects experiencing influenza related complications will be summarized by age group and treatment group.

Subject disposition will be presented for all subjects. The number of subjects who completed the study and discontinued from the study will be provided. The reasons for early discontinuation also will be presented.

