# 2.2. SCHEDULE OF EVENTS/STUDY VISITS

Assessments	Screening 	Baseline  Pre-Dose	Day 1  Post-Dose	Day 3 	Day 7 (±2 day)	Day 14  (±3 day)	End of Study Early Withdrawal 
Informed Consent	X						
Inclusion/Exclusion Criteria	X						
Pregnancy Test (Urine) 	X				X		X
Medical History	X						
Body Temperature 	X	X	X	X	X	X	X
Physical Exam		X					
Influenza-related complications (IRC) checklist 		X		X	X	X	X
Vital Signs 		X		X	X	X	X
Concomitant Medications Review 	X	X	X	X	X	X	X
Clinical Chemistries and Hematology 		X			X		X
Urinalysis 		X			X		X
Assessment of influenza symptoms/ activities of daily living/ eating habits 		X	X	X	X	X	X
Subject Diary Completion/ Review 		X	X	X	X	X	X
Nasal swabs for Virology Analysis 		X		X	X	X	X
Study Drug Administration 		X					
Serum sample for influenza antibody analysis 		X			X		
Pharmacokinetic (PK) Sampling 			X				
Adverse Events			X	X	X	X 	$X^{16}$

Study Measurements and Visit Schedule Figure Legend on Next Page

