#### **6.3.3.** Clinical Laboratory Assessments

Descriptive summaries of the following selected (quantitative) clinical laboratory results will be presented by study visit and treatment group for each age group and overall: ALT, AST, Serum Creatinine, BUN, HGB, Albumin, and Alkaline Phosphatase. Laboratory abnormalities (toxicities) will be graded according to the DAIDS Table for Grading Adverse Events for Adults and Pediatrics (Publish Date: December 2004). The number and percentage of subjects experiencing treatment-emergent graded toxicities will be summarized by treatment group for each age group and overall. Laboratory toxicity shifts from baseline to Day 7 will be summarized by treatment group for each age group and overall.

All laboratory toxicities that occurred before the initiation of study treatment or more than 14 days post study drug discontinuation will be excluded from the tables but will be included in the listings.

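### Labs at a withdrawal visit before Day 7 are optional and depend on the pre-dose baseline result, other sections say otherwise, and the SAP shift tables stop at Day 7

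*Protocol*

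**What the plan says.** Protocol 7.1.1 counts laboratory results among the study's main safety measures: "The primary endpoints of this study will be assessment of adverse events, laboratory analyses (clinical chemistry, hematology and urinalysis), vital signs and physical examinations". Scheduled sampling is sparse. Section 11.2.1 states: "Blood samples for clinical chemistry profiles will be collected at Baseline and at the Day 7 follow-up assessment", and 11.2.2 and 11.2.3 give the same two time points for hematology and urinalysis.

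The full Early Withdrawal visit is for children who leave before Day 7. For that visit, 10.2.2.6 opens its laboratory bullet with "If previous lab results are abnormal and considered clinically significant by the Investigator or significantly changed from baseline, blood specimen collection for clinical chemistry", and a parallel bullet covers urinalysis. Table 1 attaches footnote 17 to the laboratory cells of both the Day 14 and the Early Withdrawal columns. When the condition is met, the footnote says only "blood specimen collection for clinical chemistry or clinical hematology tests as specified in Sections 11.2.1 and 11.2.2 may be drawn".

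Three other places read differently:
- Protocol 8.3, on withdrawals before Day 7, says, as far as this is feasible: "all scheduled end-of-study assessments (including the Early Withdrawal Visit) should be performed on all participating subjects who withdraw from the study".
- Protocol 10.1 says that laboratory samples are taken at baseline and at the final study visit, without a condition.
- In the SAP 2.2 schedule, the rows for "Clinical Chemistries and Hematology" and for urinalysis carry a mark in the Early Withdrawal column with no condition.

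On analysis, protocol 13.9 says: "Laboratory toxicity shifts from baseline to post-baseline assessments will be summarized by age group and treatment group". SAP 6.3.3 says: "Laboratory toxicity shifts from baseline to Day 7 will be summarized by treatment group for each age group and overall".

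**The concern.** The condition makes sense at Day 14, because a Day 7 result then exists and the question is whether to repeat it. The same condition at a visit held before Day 7 has almost nothing to act on. It refers back to a sample taken before any drug was given, and withdrawal because of an adverse event does not trigger it. The nasal swab for secondary virology is listed at the same visit with no condition.

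At stake is the completeness of one component of the primary safety endpoint. Day 7 is the only scheduled post-dose laboratory time point, withdrawn children are not replaced (protocol 8.3), and the SAP imputes no missing laboratory values (4.3.4). Some age-by-treatment cells are small enough for one missing child to matter. Different sites may also act on different sections of the same protocol.

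**Working it through.** No figure in the plan has to be reproduced. The check sets the texts side by side and then illustrates the size.

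**1. Which earlier result can meet the condition before Day 7?** Scheduled labs are Baseline (pre-dose) and Day 7. A child at an Early Withdrawal visit has, from scheduled data, the baseline result only.
- Limb one, a result judged abnormal and clinically significant: it can be met only by the pre-dose sample.
- Limb two, a significant change from baseline: it cannot be met from scheduled data, because there is no second value. An unscheduled sample could meet it.
- If either limb is met, sampling is permitted but not required.

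**2. Do the sections agree?**
- Table 1, footnote 17 and protocol 10.2.2.6: conditional and optional.
- Protocol 8.3: all scheduled end-of-study assessments, as far as possible.
- Protocol 10.1: labs at the final study visit.
- SAP 2.2: labs at Early Withdrawal, unconditional, and none at Day 14.

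The SAP carries a July 2016 page date and refers to protocol version 4.0, while the protocol is version 6.0. The SAP schedule may therefore predate footnote 17. Sections 8.3 and 10.1 are in the current protocol.

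**3. Where would an Early Withdrawal result go if it were taken?**
- Shift tables: SAP 6.3.3 stops at Day 7. SAP 4.3.6 displays visits under their nominal CRF label and has no rule that moves an Early Withdrawal sample into Day 7. Early Withdrawal results and Day 14 repeats therefore fall outside these tables.
- Treatment-emergent toxicity table: SAP 4.3.8 counts any post-baseline visit up to 14 days after the last dose, so results within that window are included.
- Listings: all collected data are included (SAP 6).
- Declaration: SAP section 7 names only the antipyretic-dose analysis as a change and anticipates no others.

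**4. Size, for illustration only.** No document gives a withdrawal rate, so 1% to 10% is an assumption.
- Whole study: 140 × 0.01 = 1.4; 140 × 0.02 = 2.8; 140 × 0.05 = 7; 140 × 0.10 = 14 children.
- Comparator cells at 4:1: 40/5 = 8 oseltamivir subjects aged 7 to <13 years, and 30/5 = 6 aged 13 to <18 years. One child without labs is 1/8 = 12.5% or 1/6 = 16.7% of the cell.
- Birth to <28 days, up to 10 children: one is 10%.
- Chance of at least one early withdrawal among those 8 + 6 = 14 oseltamivir subjects, 1 − (1 − p)^14: 13% at p = 1%, 25% at 2%, 51% at 5%, 77% at 10%.

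**5. What a change to collection can still reach.** The synopsis notes that the cohorts above 7 years were full at amendment 3. The younger cohorts total at most 10 + 20 + 10 + 30 = 70 children, some already enrolled. At 1% to 10% that is 0.7 to 7 children.

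**The case against.** The case on the other side has real weight.

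- A reader might infer that early withdrawals, including those for an adverse event, leave no post-dose laboratory data. The documents do not support this. Footnote 16 allows further follow-up visits for an unresolved adverse event or laboratory finding. Section 11.1.2 asks that unresolved events be followed, 11.1.1.1 foresees unscheduled diagnostic procedures, and 11.2 covers hospital laboratory results. What is missing is a scheduled sample. Clinically prompted tests are not a full substitute, because a silent change prompts no test.
- A reader might also infer that abnormality rates are biased toward safety. This is plausible but not shown. One could apply the 21.4% rate of decreased neutrophil count from the earlier pediatric study to the withdrawn children and count missed cases. That assumes they have the same rate as everyone else, and in that case the percentage loses precision but is not biased. No document figure indicates a higher rate among withdrawals. Peramivir is a single dose, so a child has no need to leave in order to stop it.
- Section 8.3 speaks of scheduled assessments. It could be read as asking only for what Table 1 schedules at Early Withdrawal, which is the conditional labs. Section 10.1 may be loose wording, since the matching sentence in the synopsis names Day 7. Both readings are possible, and that ambiguity is itself a reason to reconcile the text.
- Late results are not lost to analysis altogether, as step 3 shows. The study is also descriptive and tests no hypothesis. Adverse events and vital signs are still collected at the Early Withdrawal visit.

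**Conclusion.** The point stands as an inconsistency with a practical consequence. Under Table 1, footnote 17 and 10.2.2.6, a child with an unremarkable baseline who withdraws before Day 7 has no protocol-scheduled post-dose chemistry, hematology or urinalysis. On a plain reading, protocol 8.3 and 10.1 and the SAP schedule call for those samples. The SAP schedule is the weakest of the three as authority because of its date.

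The shift-table point is separate and also stands. Relative to the current protocol, SAP 6.3.3 is narrower and the difference is not declared. Only the shift tables are affected.

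The number of children is unknown. The range of about 1 to 14 of 140 rests wholly on an assumed 1% to 10% withdrawal rate before Day 7, and it is an upper count because a clinically significant baseline abnormality or an unscheduled test could still yield a sample. The documents do not establish a direction or size of bias. The matter should be corrected; it does not undermine the study.

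**What to change.** **Protocol.** Reconcile Table 1, footnote 17 and 10.2.2.6 with 8.3 and 10.1, so that chemistry, hematology and urinalysis at an Early Withdrawal visit before Day 7 do not depend on the baseline result. Keep the conditional wording for Day 14 repeats. State in 10.1 which visit is meant by the final one.

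**SAP.** Bring the 2.2 schedule into line with the reconciled protocol. In 6.3.3, summarize shifts from baseline to the worst post-baseline value, including Early Withdrawal and Day 14 samples, as protocol 13.9 implies. Report, by treatment and age group, the number of treated children with no post-baseline lab. If the Day 7 restriction is intended, declare it in section 7. The shift-table titles in section 10 do not mention Day 7 and need no change.

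**Cost.** This needs a protocol clarification, SAP wording and a small programming change. For families, it means one blood draw in a few withdrawing children who agree to the visit, in place of the Day 7 draw they miss. The collection change helps only children still to be enrolled. The SAP changes also cover those already in the study.
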